# STUDY PROTOCOL AND STATISTICAL ANALYSIS PLAN

PROJECT TITLE: Mobile Web-based Behavioral Intervention for  
Improving Caregiver Well-being

Date: 9/1/2019

NCT Number: NCT03506945

PROTOCOL ID: 180454

PROJECT TITLE
Mobile web-based behavioral intervention for improving caregiver
PRINCIPAL INVESTIGATOR
[name]
DURATION OF THE STUDY
5 years
LAY LANGUAGE SUMMARY OR SYNOPSIS
Caregivers of persons with dementia suffer great amounts of distress that significantly impacts their mental and physical well-being, and ability to care for the patient at home without resort to nursing home placement. Yet, caregivers' access to quality, evidence-based interventions to assist them is currently very limited. We propose to test the efficacy of a web-based Behavioral Activation intervention called the Pleasant Events Project (mPEP) that has potential to significantly improve caregiver well-being.
SPECIFIC AIMS
Aim 1: Test the efficacy of wBA for improving caregiver well-being.
H1: Caregivers receiving the mPEP intervention will report improved positive affect, reduced negative affect, and improved mental and physical well-being compared to caregivers receiving a web-based bibliotherapy intervention.
Aim 2: Assess mechanisms of the mPEP intervention that promote well-being.
H2: Via data collected in the web-based portal, greater engagement in pleasant activities (i.e., treatment adherence) will be associated with greater improvement of caregiver well-being outcomes.
Aim 3: Assess the influence of the mPEP intervention for promoting physical health.
H3: Caregivers assigned to the mPEP intervention will show greater reduction in blood pressure relative to those assigned to a web-based bibliotherapy intervention.
BACKGROUND AND SIGNIFICANCE

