## **Measures**

***Blood Pressure:*** Blood pressure will be collected using an Omron HEM 907XL IntelliSense Professional Digital Blood Pressure Monitor sent to participants using US Mail or similar format. Blood pressure will be self-assessed by participants at baseline, 3-, 9-, and 15-months.

The following section details the information to be collected from caregivers via online administration. Further, we detail the specific time-points at which the information will be collected:

***Depressive Symptoms (Primary Outcome):*** Symptoms of depression will be assessed using the Center for Epidemiological Studies Depression Scale—Revised (CESD-R). The CESD-R is a 20-item scale that asks patients to rate the degree to which they have experienced several symptoms of depression over the past week. Scores of  $\geq 16$  correlate highly with a diagnosis of depression. The scale was revised to better reflect the diagnostic criteria of the DSM-5, and the scale continues to good psychometric properties. This scale addresses RFA-AG-18-030, as depressive symptoms is a key well-being outcome in caregivers. This scale will be administered at baseline, 3-, 9-, and 15-months.

***Positive and Negative Affect.*** We will utilize the Positive and Negative Affect Schedule (PANAS) to assess positive (PA) and negative affect (NA). The PANAS contains 20 items assessing PA and NA. Alpha reliability is excellent, ranging from .83-.90 for the PA scale and .85-.90 for NA. This scale addresses RFA-AG-18-030, which lists positive and negative affect as key outcomes to be assessed. This scale will be administered at baseline, 3-, 9-, and 15-months.

***Mental and Physical Well-Being:*** Mental and physical well-being will be assessed using the SF-12 scale, which is a multi-purpose, short form health survey consisting of 12 questions. Test-retest and internal reliability exceed 0.70 in studies of this scale's psychometric properties. The SF-36 also has excellent content, criterion, and predictive validity. This scale will be administered at baseline, 3-, 9-, and 15-months.

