A key element to keep participants engaged in the program is the use of text reminders. Each night, at a time of the participant’s choosing, a text is sent to participants with a hyperlink to their individualized web-portals. Along with the hyperlink is a message asking users to provide an update on their progress toward their goals for the week. In addition, for the first three months of using the mPEP intervention, participants will receive bi-monthly 10-minute “check-in” calls from a coach to answer questions on how to use the web site, problem-solve any barriers to participating in activities, and encourage participants to do their best to achieve their weekly goals. So as not to overburden caregivers, these check-in calls will be scheduled between the coach and caregiver at a time of the caregiver’s choosing. Participants complete a total of three phases in the project, which are (sample screen shots presented in Figure 3):

**Phase 1:** This phase involves self-monitoring activities over the course of one week. This phase is designed to capture activities the participants already engages in (and when), to help increase awareness of how balanced their lives are with regard to self-care activities vs caregiving activities. At the end of each day, participants complete an activity detailing when they woke up, activities they completed throughout the course of the day, and ratings of how enjoyable/pleasant each activity was. Each activity is entered into a personalized calendar so

they can visually see how they spent their day, as well as how many hearts they received from each activity.

**Phases 2 and 3:** These phases involve the selection and engagement in activities designed to promote overall well-being for the caregiver. In Phase 2, the participant completes a mood questionnaire of their positive and negative affect over the previous week. This is designed to provide participants with a baseline assessment of their well-being, on which to track progress as they move through the stages of the application. Following completion of the questionnaire, the participant receives feedback on all activities during phase 1 that were rated

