as at least moderately pleasurable (i.e., rated as 3 hearts). Then, the participant will be provided with a structured group of tasks to help identify treatment goals, including: a) select new activities from several life domains (e.g., hobbies) that may increase access to rewarding experiences, and b) create a weekly goal for “hearts” designed to help participants start with achievable activities that are most likely to produce successful attainment of goals. This helps maintain motivation by taking a stepwise goal-setting approach while helping reduce barriers to treatment compliance. During phase 3, participants track their daily engagement in activities, with each participated activity adding to their weekly hearts goal. At the completion of one week of activities, participants again complete their weekly mood questionnaire. Participants then see their weekly accomplishment

s for hearts achieved and overall mood score. The mPEP algorithm then computes the following week’s hearts goal based on hearts achieved and overall mood. Finally, participants

repeat phases 2 and 3 until completion of the program.

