**Power Analysis:** Because the mPEP intervention is based upon our in-person version of PEP for caregivers, we anticipate effect sizes to be comparable to those seen in our previous trials. Accordingly, we powered our study based results showing an effect size of 0.4 (small to moderate) in favor of mPEP with an active comparator. Sample size estimates were based on the Hedeker, et al. method for various covariance structures for mixed effects models. For the proposed study, we assumed an autoregressive covariance structure, with a correlation between sequential assessments set at 0.5 based on our previous trial in caregivers. Using this methodology, assuming an alpha level of 0.05, we have a minimum 90% power to detect an effect size of 0.4 with 15% attrition between each time-point (39% cumulative drop-out rate), when there are 100 subjects per each condition.

**Hypothesis 2:** Greater treatment-associated change in behavioral activation will be associated with greater improvement of caregiver well-being outcomes.

**Statistical Analysis:** For this hypothesis, multilevel (mixed) models will be used. To test for mediation, we will utilize the analytic strategy described by Krull and MacKinnon. In this approach, four conditions are tested: a) the relationship between intervention condition and the dependent variables (e.g. Depressive symptoms), b) the relationship between intervention condition and mediator (behavioral activation), c) the relationship between behavioral activation and the outcome, and d) the relationship between intervention condition and outcome after controlling for the proposed mediator. Mediation will be tested using the Monte Carlo Method for Assessing Mediation (MCMM). **Power Analysis:** The proposed study will be powered to detect if treatment-related change in behavioral activation mediates treatment-related change in depressive symptoms. Therefore, power is based upon the strength of both the 'a' path (i.e., mPEP significantly increases behavioral activation relative to our control condition) and 'b' path (i.e., change in behavioral activation is significantly associated with change in depressive symptoms). As per our pilot data, we conservatively estimate a small-to-medium effect ( $r=.20$ ) between mPEP and behavioral activation ( $r=.20$ ) between mPEP and

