depressive symptoms, and a medium effect ( $r=.50$ ) between change in behavioral activation and change in depressive symptoms. With  $N = 200$  and alpha of 0.05, we have 81% power to detect a significant mediation effect. These power estimates are based on 15% attrition between time-points (39% overall project attrition).

**Hypothesis 3:** Caregivers assigned to the mPEP intervention will show greater reduction in blood pressure relative to those assigned to a web-based bibliotherapy intervention.

Dependent Variables: Systolic and Diastolic Blood Pressure. Independent Variables: Condition and Time (Baseline, 3-, 9-, and 15-months). Moderator: Age.

**Statistical Analysis:** This hypothesis will be tested using GAMMs. Condition will be entered into the model as a fixed-effect predictor along with time and their interaction. Because age is a known predictor of blood pressure we will enter age as a covariate and moderator of treatment efficacy in analyses. If the smoothed interaction of treatment condition and time is significant at the .05 level (determined by an F test of the relevant coefficients in the model) we will test all pairwise differences with Westfall-Young adjusted p values. **Power Analysis:** Power estimates were calculated using the Hedeker, et al. method for various covariance structures for mixed effects models. For the proposed study, we assumed an autoregressive covariance structure. An estimated correlation of 0.4 was assumed between sequential assessments based on our pilot data. Using this methodology, assuming an alpha level of 0.05 and 200 subjects (100 per treatment arm), and 15% attrition between time-points (39% cumulative dropout across time-points), we have 80% power to detect a small-to-medium effect size of 0.32.

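### The H2 mediation test needs behavioral activation measured in both arms, but the plan describes activation data only for mPEP; its 81% power also needs all 200 participants analysed

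*Combined protocol and SAP*

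**What the plan says.** The hypothesis is worded in two ways. Under Specific Aims, Aim 2, it reads "Via data collected in the web-based portal, greater engagement in pleasant activities (i.e., treatment adherence) will be associated with greater improvement". Under Statistical Analyses it becomes "Greater treatment-associated change in behavioral activation will be associated with greater improvement of caregiver well-being outcomes", to be tested as mediation under four conditions. Condition (b) relates arm to activation, and condition (d) is the arm effect on the outcome after adjustment for activation. The power paragraph describes the a path as "mPEP significantly increases behavioral activation relative to our control condition" and concludes that "we have 81% power to detect a significant mediation effect", with N = 200 and alpha 0.05. It adds that the estimates reflect 15% attrition between time points, 39% overall.

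Activity recording appears in the description of the mPEP arm. Of Phase 1 it says "This phase is designed to capture activities the participants already engages in", and later "During phase 3, participants track their daily engagement in activities, with each participated activity adding to their weekly hearts goal". For the Information and Support arm, the personal log-in is said to yield compliance and exposure data, with content opened and time logged in as examples. The survey list under Measures is introduced with "The following section details the information to be collected from caregivers via online administration".

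**The concern.** An arm-by-mediator comparison needs a mediator score for every arm. Time spent on a resource guide does not measure engagement in pleasant activities, and hearts are assigned to each caregiver's own chosen activities within the mPEP app. If controls have no activation score, conditions (b) and (d) and the product a × b cannot be computed, so the analysis for which 81% power is claimed cannot be run.

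What would survive is H2 as worded under Specific Aims: among mPEP users, those who did more may have improved more. That is not a randomised comparison. Data on activation that are not collected at the time, baseline scores above all, cannot be recovered later.

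**Working it through.** **1. Where the document describes activation data**

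| Source | Arm | Content | Activation score? |
|---|---|---|---|
| mPEP Phases 1 to 3 (Interventions, a) | mPEP | daily activities, hearts | yes |
| Control site log-in (Interventions, b) | control | compliance and exposure to information | no |
| Measures: blood pressure, CESD-R, PANAS, SF-12, ZBI, CDR, ADLQ, RMBPC | both | outcomes, stress, care-recipient status | no |
| Measures: Role Overload | said to be given through the mPEP program, so control coverage is unclear | daily stress | no |

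The first activity record described is Phase 1 of the assigned mPEP program, so no activation baseline outside mPEP is described for a change score. Condition (a), arm against outcome, is unaffected. Condition (c), activation against outcome, could be estimated within mPEP. Conditions (b) and (d) could not be estimated.

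**2. Reproducing the 81%**

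Inputs from the Hypothesis 2 power paragraph: r = 0.20 (arm with activation), r = 0.50 (change in activation with change in depression), N = 200, alpha 0.05; two-sided as stated at the start of Statistical Analyses. Fisher z:

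power = Φ(atanh(r) × √(N − 3) − 1.96)

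- a path: atanh(0.20) = 0.2027; √197 = 14.04; product 2.845; Φ(0.885) = 81.2%.
- b path: atanh(0.50) = 0.5493; product 7.71; power above 99.9%.
- Both significant: 81.2%.

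Simulating the Monte Carlo interval for a × b gives about 83%. The stated figure is therefore essentially the power of the between-arm contrast in activation with all 200 measured.

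**3. Attrition**

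Retention is 0.85³ = 0.614, a 39% loss. For a test at a single follow-up with r = 0.20:

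| Follow-up | N | a-path power |
|---|---|---|
| none lost | 200 | 81.2% |
| first (200 × 0.85) | 170 | 74.5% |
| second (200 × 0.85²) | 144 | 67.3% |
| third (200 × 0.85³) | 122 to 123 | 59.9% to 60.3% |

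The b path stays above 99.9% throughout, so these are also the joint powers. Simulated Monte Carlo intervals at N = 122 gave 62% to 67%.

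**4. What a two-arm scale with repeated measures could give**

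Assumptions: d = 2r/√(1 − r²) = 0.408; SD 1; AR(1) correlation ρ; one common arm difference estimated over three follow-ups; 15% loss before each. Per arm, 12.75, 10.84 and 61.41 participants have one, two and three follow-ups. A participant with k follow-ups contributes information (k − (k − 2)ρ)/(1 + ρ).

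At ρ = 0.5 (the H1 value, borrowed): 12.75 × 1 + 10.84 × 1.333 + 61.41 × 1.667 = 129.6. SE = √(2/129.6) = 0.124; z = 0.408/0.124 = 3.29; power Φ(3.29 − 1.96) = 90.8%.

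If the effect fades to 75% and then 50%, the information-weighted difference at ρ = 0.5 is 0.322; z = 2.59; power 74%.

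| ρ | SE | Constant effect | Fading 100/75/50% |
|---|---|---|---|
| 0.3 | 0.113 | 95.1% | 81% |
| 0.5 | 0.124 | 90.8% | 74% |
| 0.8 | 0.142 | 82.2% | 63% |

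These figures are for the a path only. Fading is plausible because check-in calls are planned only for the first three months, but the document gives no effect pattern over time.

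**The case against.** The strongest reply is that this argues from silence. The plan takes r = 0.20 between mPEP and activation from pilot data and defines the a path against control, so its writers clearly intended a two-arm mediator and may already have an instrument. The control-site data are introduced by examples, which leaves room for more. This stands as far as it goes: a reader might infer that controls are certainly unmeasured, and no section says so. It does not clear the plan, because the mediator of a powered hypothesis then has no named instrument, arm coverage or schedule, while other constructs have all three.

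It can also be said that H2 concerns only mPEP users. The Aim 2 wording allows this; the four conditions and the power paragraph do not.

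On power, mixed models use partial follow-up, so the completer figure of about 60% need not be the trial's power. That is fair. A reader might infer that the 81% is a miscalculation, but it reproduces from the stated correlations at N = 200. What does not fit is the statement that it already reflects 39% attrition.

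Finally, the survey is already long and fatigue is a listed risk, so adding a scale has a cost.

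**Conclusion.** The point holds as an inference from the listed data, with medium confidence. No activation source is described for 100 of the 200 participants. If the list is complete, the a path, condition (d) and the indirect effect cannot be estimated. The 81% is a-path power with all 200 analysed; single-visit tests under the plan's own attrition have about 75%, 67% and 60%.

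It would be tempting to conclude that adding a scale restores both the claimed power and a randomised mediation result. Neither follows. Repeated-measures a-path power is 82% to 95% if the effect is constant but 63% to 81% under the assumed fade. Only the a path is randomised: the path from activation to depression stays observational even with a two-arm scale. This should be fixed, but it touches Aim 2 only; the H1 and H3 comparisons are unaffected.

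**What to change.** 1. If a two-arm activation measure is already collected, name it as the H2 mediator and give its control-arm schedule. If not, add one short self-report activation or pleasant-activity scale to the online survey in both arms at baseline, 3, 9 and 15 months, the schedule under Measures. For participants who started without a baseline score, compare post-baseline levels between arms.
2. Restate the 81% for the numbers expected to be measured and the model to be used, showing a range over correlation and effect pattern.
3. State that only the a path is randomised, and relate activation at one visit to depression at a later one. The plan's 0.50 is for change against change, so a lagged analysis needs its own assumed value.
4. Only if no two-arm measure is possible, delete the mediation test and the 81%, and restate H2 as an exploratory association within mPEP. Note there that weekly hearts goals adapt to mood, so adjusting for prior mood does not make the association causal.

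Cost: one sentence if a measure exists. Otherwise, a few more minutes on an assessment of up to 2 hours (Compensation for Participation), possible slight prompting of controls, self-report that may differ from app logs, and missing baselines for anyone already started. Option 4 changes wording only but gives up the mediation claim.

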**Statistical Analyses:** All hypotheses will be two-sided at the 0.05 level and intent-to-treat with data included for all subjects completing at least one post-baseline assessment. Data analyses will employ generalized additive mixed models (GAMMs) tailored for longitudinal data. GAMMs allow for potentially nonlinear effects of independent variables on outcomes; the nature of the nonlinearity and degree of smoothness is data-determined for each independent variable. Models will include as covariates variables that differ significantly by condition. We will use Akaike Information Criterion (AIC) to determine covariance structures and variable selection. To control for inflated Type I error rates from multiple testing within each hypothesis, we will use the Westfall-Young step down maxT randomization procedure, which adjusts p-values for significance in multiple comparisons while taking into account the correlation of the outcomes. In this way we can control for an overall family-wise error rate of .05 while achieving more power than Bonferroni adjustments. **Missing Data:** Follow-up data will be obtained on all participants, regardless of treatment completion. We will perform sensitivity analyses for impact of potentially informative missing data via pattern mixture models extended to incorporate random effects. We anticipate 15% dropout between each time point, accounting for an overall (cumulative) dropout rate of 39%.

**Hypothesis testing: Hypothesis 1:** Caregivers receiving mPEP will report reduced depression, improved positive affect, reduced negative affect, and improved well-being compared to caregivers receiving a web-based bibliotherapy intervention. **Dependent Variables:** Depressive Symptoms, Positive and Negative Affect; SF-36 scores. **Independent Variables:** Condition and Time (Baseline, 3-, 9-, and 15-months). **Statistical Analysis:** This hypothesis will use GAMMs. Condition will be entered as a fixed-effect predictor along with time and their interaction. If the smoothed interaction of condition x time is significant at the .05 level (determined by an F test of relevant coefficients in the model) we will test for pairwise differences with Westfall-Young adjusted p values.

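### Hypothesis 2's 81% mediation power is said to allow for 39% attrition, but its stated inputs give 81% only with complete data on all 200 caregivers

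*Combined protocol and SAP*

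**What the plan says.** The relevant text is in the combined protocol and SAP, Statistical Analyses, under Hypothesis 2. The power paragraph rests power on two paths: condition to behavioral activation (r = .20), and change in activation to change in depressive symptoms (r = .50). It also gives r = .20 between condition and depressive symptoms. With N = 200 and alpha 0.05 it concludes that "we have 81% power to detect a significant mediation effect". It then adds: "These power estimates are based on 15% attrition between time-points (39% overall project attrition".

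For the analysis itself, "multilevel (mixed) models will be used", and "Mediation will be tested using the Monte Carlo Method for Assessing Mediation (MCMM". The general paragraph of Statistical Analyses makes tests two-sided, with "data included for all subjects completing at least one post-baseline assessment".

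The power paragraphs for Hypotheses 1 and 3 name a method for mixed models, an autoregressive structure and a correlation. Hypothesis 1 works "with a correlation between sequential assessments set at 0.5 based on our previous trial in caregivers". For Hypothesis 3, "An estimated correlation of 0.4 was assumed between sequential assessments based on our pilot data". The Hypothesis 2 power paragraph gives no within-person correlation, covariance structure, contrast or time point.

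**The concern.** An r of .20 in 200 people has about 81% power at two-sided .05 with nobody missing. The stated figure therefore matches a complete-data calculation, while the sentence after it says that 39% attrition is already built in. Both can be true only if something not stated for Hypothesis 2, such as gain from repeated measurements, offsets the loss.

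Aim 2 is one of three specific aims, and the plan says the study will be powered for this mediation effect. A reader would take 81% as the power left after dropout. If the real figure is lower, a null mediation result could be over-read as evidence against the proposed mechanism.

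**Working it through.** **Inputs.** From Hypothesis 2: r = .20 (the a path), r = .50 (the b path), r = .20 (condition with symptoms), N = 200, alpha .05. From the general paragraph: two-sided tests. Retention at 15% loss per interval is 200 × .85 = 170 at 3 months and 200 × .85³ = 122.8 at 15 months; 1 − .85³ = 38.6%, the plan's 39%.

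**Step 1: which path limits power.** For the b path, adjusted for condition, the partial correlation is (.50 − .20 × .20)/(1 − .20²) = .46/.96 = .479. Its power exceeds 99.9% even at n = 122, so the a path sets the result.

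**Step 2: reproduce 81%, one change score per person.** Fisher z: power = Φ(atanh(.20) × √(n − 3) − 1.96), with atanh(.20) = .2027.

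- n = 200: .2027 × √197 = 2.846; Φ(0.886) = 81.2%
- n = 170: .2027 × √167 = 2.620; Φ(0.660) = 74.5%
- n = 122: .2027 × √119 = 2.212; Φ(0.252) = 59.9%

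The noncentral t (df n − 2, noncentrality .20√n/√.96) gives 81.9%, 75.4% and 60.9%. Simulating the Monte Carlo mediation test with all three stated correlations gives 81.1% to 82.6% at n = 200, 75.3% to 75.8% at n = 170 and about 61% at n = 122. The stated 81% is reproduced with all 200 analysed, and not at 170 or 122.

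**Step 3: could repeated measures restore it?** Hypothesis 2 states no within-person correlation, so as an assumption I borrow 0.5 from Hypothesis 1 and 0.4 from Hypothesis 3. The effect is d = 2 × .20/√(1 − .04) = .408, with 100 per arm and follow-up at 3, 9 and 15 months. Dropout is monotone: 15% have no follow-up visit, 12.75% one, 10.84% two and 61.4% three. With a known AR(1) covariance V, information per arm is the sum over dropout patterns of n_k × V_k⁻¹. The variance of the arm difference is twice the inverse, and power = Φ(.408/SE − 1.96).

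| Contrast on the a path | SE, AR(1) 0.5 | Power | SE, AR(1) 0.4 | Power |
|---|---|---|---|---|
| 15 months | .176 | 63.9% | .178 | 63.1% |
| Mean of 9 and 15 months | .145 | 80.3% | .142 | 82.2% |
| Constant effect, three visits | .124 | 90.8% | .119 | 93.1% |

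Depending on the contrast, power after the plan's attrition runs from about 63% to 93%, and one contrast lies close to 81%.

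**Step 4: can Hypotheses 1 and 3 identify the convention?** A constant effect over three follow-ups gives Φ(.40/.1242 − 1.96) = 89.6% for Hypothesis 1, against a stated minimum of 90%. For Hypothesis 3 it gives Φ(.32/.1186 − 1.96) = 77.0%, against a stated 80%. Using four time points with a complete first visit gives 96% and 88%. Neither version reproduces both stated figures.

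**The case against.** The strongest reply is that the planned analysis is a multilevel model, which keeps information from people who drop out later, so single-score arithmetic is the wrong test. This largely stands. Under the plan's own attrition, averaging 9 and 15 months gives 80.3% or 82.2% with the two correlations stated elsewhere in the plan. Borrowing 0.5 is reasonable, because depressive symptoms are also a Hypothesis 1 outcome. Aim 2 also takes activity data from the web portal, so the mediator may be recorded more often than the visit schedule suggests. None of this appears in the Hypothesis 2 power paragraph, so a reader must choose unstated inputs to arrive at 81%.

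Three stronger readings are tempting, and the documents do not support them.

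- **Dropout was ignored.** Quoting N = 200 does not show this. Hypotheses 1 and 3 also quote enrolled numbers beside an attrition allowance; Hypothesis 1, for instance, says "we have a minimum 90% power to detect an effect size of 0.4 with 15% attrition between each time-point". The match at n = 200 is suggestive only.
- **True power is about 60%.** That figure assumes one score per 15-month completer. The plan analyses anyone with at least one post-baseline assessment, about 170 people if 15% are lost before 3 months.
- **By Hypothesis 1's convention the answer should be 91%.** The convention that comes close for Hypothesis 1 misses Hypothesis 3 by three points, so it cannot be taken as the plan's method.

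It is also fair to say that the consequence is limited: Hypothesis 2 concerns mechanism, and the sample size has its own justification under Hypothesis 1.

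**Conclusion.** The point holds as a power figure whose stated attrition basis does not follow from its stated inputs. Those inputs give about 81–82% with 200 complete, about 75% at 170 and about 60–61% at 122, using one change score per person. Power for the planned model after dropout could be well below or well above 81%, roughly 63–93% in the cases tried, so the figure is neither confirmed nor proven too high.

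This rests on the Monte Carlo test of the indirect effect deciding the hypothesis, rather than a requirement that all four listed conditions be significant. The 63–93% range further assumes borrowed correlations, monotone dropout, a known covariance and an r of .20 that applies to each contrast. The point should be fixed because the plan makes a specific claim about a stated aim. It does not affect the Hypothesis 1 test.

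**What to change.** Recompute Hypothesis 2 power for the planned multilevel Monte Carlo mediation test with 15% attrition per interval. State the within-person correlation, covariance structure and contrast (with its time point or points), and replace 81% with the result.

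If the attrition basis cannot be shown, label 81% as a complete-data figure (N = 200, no dropout) and remove the attrition sentence from the Hypothesis 2 paragraph.

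The cost is one power calculation, or a wording change. No participants are added, and enrolment, conduct and the Hypothesis 1 test are unchanged. The downside is that the stated power for Aim 2 may look less favourable.
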